## 2. ABSTRACT

**Introduction:** Coronavirus Disease 2019 (COVID-19) has caused a global pandemic. Epidemiological and clinical inter-individual differences, symptomatology, recovery and humoral response against Severe Acute Respiratory Syndrome Coronavirus 2 (SARS-CoV-2) are key factors to better understand and predict the course of the pandemic. As Health Care Workers (HCWs) are caring for infected patients they are more susceptible to infection, which not only is critical for their own health but also because it results in a shortage of HCWs that seriously affects health services. Thus, maintaining the health and welfare of HCWs and enabling their rapid return to work is vital to overcome this crisis. The ProHEPiC-19 cohort presents data on the immune response of HCWs infected with SARS-CoV-2. This dynamic cohort was started in March 2020 and still continues including participants.

**Objectives:**

**Primary:** To consolidate a prospective cohort of Health Care Workers (HCWs) to generate epidemiological and clinical high quality data. This information will be relevant to improve health policies and clinical COVID-19 protocols. This cohort will also be used as an ongoing platform to implement SARS-CoV-2 research projects with particular emphasis on incidence rate, reinfection, vaccines, and long term immune response.

**Secondary:**

1. To determine the kinetics of SARS-CoV-2 antibodies and cellular immune response in early, mid, and long periods of immunization.
2. To assess the relation between clinical variables and initial RT-PCR results with the interindividual differences in the immune response in early, mid, and long periods of immunization.
3. To analyze differentially expressed cytokines as biomarkers of disease progression in early, mid, and long periods of immunization.

**Methods and analysis:** Longitudinal, dynamic, prospective cohort study with a 12-month follow-up, which is being conducted in 4 primary-care centres and one hospital of Northern Metropolitana Nord of Barcelona (Spain). For now, the study consists of 1350 participants divided into 2 cohorts: 1) Healthy-Exposed HCWs: 675 not infected by SARS-CoV-2 (RT-PCR with a negative result and negative SARS-CoV-2 antibodies at baseline) and 2) Infected HCWs: 675 symptomatic participants (those with new persistent cough, temperature  $\geq 37.5^{\circ}\text{C}$ , anosmia, or ageusia or other compatible symptoms with COVID-19) or asymptomatic participants diagnosed by positive RT-PCR test and/or SARS-CoV-2 antibodies (IgM, IgG at baseline). Primary outcomes include: humoral and cellular immune response, quantitative antibodies to SARS-CoV-2, SARS-CoV-2 antibody levels related to progression phenotype, clinical spectrum of SARS-CoV-2, symptomatology, demographics and other variables that may be predictive of immune response.

**Follow-up:** baseline, 15 days, 1, 3, 6, 9 and 12 months.

**Findings to date:** Current literature has shown that the immune response is maintained for a minimum of 2 months. Nevertheless little is known about the association between the immune response and the progression phenotype of COVID-19.

**Future plans:** This prospective cohort offers the possibility to study associations between immune response and progression phenotype according to age and gender as well as long-term immune response. In turn, we will be able to examine possible cumulative effects, taking into account several

clinical variables. The study is ongoing and we plan to extend it to increase the size of the cohort until 2024.

**Ethics and dissemination:** The study is approved by the Ethics Committee (IDIAPJGol ref 20/067-PCV IGTP ref COV20/00660 (PI-20-205). Dissemination will occur through presentations at National and International conferences and publications in international peer-reviewed journals.

Trial registration number: ID: 4R20-105

**Keywords:** SARS-CoV-2; COVID-19; Cohorts; Epidemiology, SARS-CoV-2 antibodies, Primary Health Care, Hospital, Health Care Workers, Immunology Response COVID-19.

### 3. STUDY GLOSSARY:

Coronavirus Disease 2019	COVID-19
Severe acute respiratory syndrome coronavirus	SARS-CoV-2
Health Care Workers	HCWs

## 4. BACKGROUND

COVID-19, caused by Severe Acute Respiratory Syndrome Coronavirus 2 (SARS-CoV-2), was declared pandemic in March 2020 by the WHO [1]. At present (March, 30, 2020), the virus has infected more than 58.537 people worldwide with an associated case mortality rate of 1% to 15%, depending on the country and age [2].

Particularly, COVID-19 has affected a very high percentage of Health Care Workers (HCWs). In fact, 26% of all individuals who tested positive for SARS-CoV-2 by PCR in Spain, where transmission of SARS-CoV-2 has been intense, were HCWs [3]. So, HCWs are a high-risk group for developing the infection, that is exceptionally relevant for three reasons: 1) because of the clinical manifestations, severe in some cases, produced by the disease itself; 2) because as HCWs are caring for infected patients, they are more susceptible not only to infection, but also to infecting co-workers, patients and family members; and 3) because infection in this group leads to absenteeism from work, reducing the number of professionals available for health care. This situation results in a shortage of HCWs that seriously affects health services. Thus, maintaining the health and welfare of HCWs and enabling their rapid return to work is vital to overcome this crisis. Furthermore, as HCWs are constantly exposed to the virus, they are an interesting group to investigate the kinetics and antibody production in early, medium and long-term immunisations against SARS-CoV-2

In fact, a major current question is if individuals who have been infected with SARS-CoV-2, whether symptomatic or asymptomatic, knowingly or unknowingly, develop permanent immunity to the virus. Answering this question is crucial for epidemiologists, policy makers, health service professionals and society at large. To do so, three different types of diagnostic tools can be used: 1) RNA-based tests to determine whether viral genes are present in nasal and throat swabs, indicating active infection (by RT-PCR); 2) Detection of antibodies against SARS-CoV-2 in plasma or capillary blood. Antibodies can also indicate active infection but, more importantly, they indicate if the individual has already been infected and is able to develop a satisfactory immune response based on the presence of these antibodies. 3) Cytokine storm testing is a more exploratory diagnostic tool that can include assessment of the presence of proinflammatory cytokines in response to SARS-CoV-2 infection. The presence of a 'cytokine storm' has been linked to disease severity and progression and to a particular feature of the pathogenic features of SARS-CoV-2 infection [4].

Different studies have shown that levels of antibody response differ depending on the clinical spectrum of SARS-CoV-1 [5]. Nevertheless, little is known regarding immune response to SARS-CoV-2. It has been observed that the highest antibody responses are presented by people with a more severe clinical spectrum, hospital admissions and intensive care units. The highest response has been shown by IgM and IgG against SARS-CoV-2 antigens [6,7]. Despite this, there are still few studies that have been able to accurately analyze the results of the immune response over a period of 12 months. However, the immune response to SARS-CoV-2 infection is heterogeneous, with clinical spectra ranging from individuals with asymptomatic infections to individuals with very severe clinical manifestations that can even lead to death. It is possible that some individuals will never develop sterilizing immunity following infection with SARS-CoV-2 or that multiple exposures will be needed for affinity maturation and development of long-lasting protection. All these points have to be explored and they are extremely important for re-vaccination criteria.

At the current stage of the pandemic, laboratory tests measuring antibody response and seroconversion remain essential. Studies on indicators of inflammatory response and the prognostic value of other Covid-19 indicators and acute phase reactants are also needed. In addition, the identification of proinflammatory biomarkers may have added value in disease prognosis and provide novel information for

the therapeutics of immunosuppression of the inflammatory process in the acute phase. Furthermore, by conducting serological studies of the population we can achieve the following objectives: 1) To obtain a dynamic, qualitative and quantitative study of the immune response to SARS-CoV-2; 2) To accurately define the infection rate of a specific affected area, which is essential to determine the mortality rate of the infection; 3) To identify individuals with strong antibody responses, who could be donors to generate convalescent serum therapies; and 4) To determine who has and who lacks immunity against the disease. This is crucial especially because this serological information can be used to strategically deploy HCW who are immune to infection, thus limiting the risk of exposure and inadvertent spread of the virus.

As mentioned above, HCWs are a high-risk group for acquiring SARS-CoV-2 infection. Some of these professionals with symptoms or with high-risk contacts are confined and unable to return to their clinical activities while awaiting the results of the (RT)-PCR tests. It should be noted that all of them are confined to their homes for a minimum period of 8 days depending on the PCR result at 8, 14 and 28 days. This is causing a shortage of HCWs, which is seriously affecting the health services and putting additional pressure on a sector already overburdened by the pandemic.

Since the initial symptoms are very non-specific and compatible with any other respiratory virus, it is very difficult to screen for other diseases. It is therefore essential to identify factors associated with the protection of professionals against SARS-CoV-2. This is essential because the evolution of the SARS-CoV-2 pandemic makes it likely that new epidemic waves will appear within a short period of time. To a large extent, the factors conditioning the evolution of the infection, the permanence of the virus and the immunity of infected persons and that of healthy carriers of the infection have not yet been clearly identified.

To date, seroprevalence studies conducted in Spain have used cross-sectional designs. Thus, they cannot provide systematic data on long-term antibody and cellular immune responses.

Thus, thorough serological and prospective studies are needed to determine whether ADE manifests among SARS-CoV-2 infections, either because of prior homologous infection or cross-reactive antibodies from other HCoVs. This will have particular relevance for vaccination plans.

Another interesting point that deserves further analysis is analyzing the different antibody specificities generated and their dynamics. Several studies have examined various types of antibodies identified against SARS-CoV-2 (Spike1, Spike2, Nucleocapsid, envelopes), identifying variable responses [8,9]. However, little is known about the simultaneous kinetics of the different antibodies over time. This can be analyzed with our cohort and also with the antigens used in the various vaccines that will be in the market in the next months. Thus, given the virus's short evolution, it is necessary to create an exhaustively monitored cohort. This cohort will make it possible to identify the kinetics of SARS-CoV-2-specific antibodies in individuals with different degrees of severity of COVID-19 and to know which levels of antibodies are protective against new possible reinfections in 3 years.

Crucially, this serological information will be used to strategically deploy HCW immune to the infection, limiting the risk of exposure and inadvertent propagation of the virus.

In conclusion, the present study is crucial to obtain epidemiological and clinical data to improve health policies for the prevention of SARS-CoV-2 infection. In addition, the study will be conducted simultaneously with the course of the pandemic, which will make it possible to obtain real-time data on the different waves that occur and, in turn, to study the SARS-CoV-2 endemic. Therefore, ProHEPIC-19 can be used as an ongoing platform to implement SARS-CoV-2 research projects with particular emphasis on incidence rate, reinfection, vaccines, and long term immune response.

## 5. HYPOTHESES AND OBJECTIVES

### 5.1 HYPOTHESES

The specific hypotheses are:

Infection with SARS-CoV-2 will produce different levels of immune response with respect to:

1. The kinetics and immune response is different depending on the clinical spectrum of COVID-19 disease.
2. The immune response is conditioned by age, sex and other clinical variables
3. Cytokines are good biomarkers to identify COVID-19 disease progression.

### 5.2 OBJECTIVES

#### 5.2.1 PRIMARY AIM

To consolidate a prospective cohort of Health Care Workers to generate epidemiological and clinical high quality data. This information will be relevant to improve health policies and clinical COVID-19 protocols. This cohort will also be used as an ongoing platform to implement SARS-CoV-2 research projects with particular emphasis on incidence rate, reinfection, vaccines, and long term immune response.

Primary Outcome Measure:

1. Creation prospective cohort of health care workers

Include 675 exposed HCW participants and 675 infected HCW participants against SARS-CoV-2, cohorts will be compared at each time point in terms of sociodemographic, epidemiological, clinical, and immunological information available. An exploratory bivariate analysis will be performed using the tests of Chi Square, ANOVA, Kruskall-Wallis, depending on the application conditions assumptions.

Time Frame: Baseline, to 12 months after the beginning of the study

2. Cohort description demographics (age, sex, academic level, housing characteristics, work variables)

Descriptive analysis of the participants will be performed using the number and percentage for categorical variables, and mean and standard deviation or median and quartiles 1 and 3 for quantitative variables, an exploratory bivariate analysis will be performed using the tests of Chi Square, ANOVA, Kruskall-Wallis, depending on the application conditions assumptions.

Time Frame: Baseline, to 12 months after the beginning of the study

2. Cohort description clinical spectrum (asymptomatic, mild-moderate illness, severe-critical)

Cohort comparison, an exploratory bivariate analysis will be performed using the tests of Chi Square, ANOVA, Kruskall-Wallis, depending on the application conditions assumptions.

[Time Frame: Baseline, to 12 months after the beginning of the study]

### 5.2.2 SECONDARY AIM

1. To determine the kinetics of SARS-CoV-2 antibodies and cellular immune response in early, mid, and long periods of immunization.
2. To assess the relation between clinical variables and initial RT-PCR results with the interindividual differences in the immune response in early, mid, and long periods of immunization.
3. To analyze differentially expressed cytokines as biomarkers of disease progression in early, mid, and long periods of immunization.

## 6. METHODS

### 6.1. DESIGN:

Dynamic prospective study conducted in two cohorts of health care workers (HCW) (healthy and infected). Each cohort will include 675 participants.

Biological, clinical, psychological and social warning signs follow-up closely monitored during one year.

### 6.2. POPULATION AND SETTING

This is a multicenter study (public primary care centers set in Mataró, Sabadell and Santa Perpètua and the public third level hospital Hospital *Germans Tries i Puig* located in Badalona) with HCW cohorts recruited from Gerència Territorial Metropolitana Nord of the Catalan Institute of Health (ICS), which consists of 7,776 HCW, including physicians, nurses, COVID-19 researchers, medical residents and other essential workers in direct contact with patients during present and future pandemic waves.

#### 6.2.1. SELECTION CRITERIA:

HCWs (physicians, nurses, auxiliars, COVID-19 researchers and other essential workers in direct contact with patients during the first, second or third wave of COVID-19) at risk of infection due to direct patient contact. Random sampling is being used for the inclusion of subjects. Different recruitment strategies are being applied to contact with participants such as email, phone calls.

Inclusion criteria:

≥ 18 years of age

Accept to take part in the study and sign the informed consent

To be a HCWs infected or exposed to SARS-CoV-2.

Exclusion criteria:

Not accepting taking part in the study and/or not to sign the informed consent

Not to be a HCW exposed to SARS-CoV-2

### 6.3. STUDY PERIOD

From March, 31 2020 until recruitment is finished (estimated on June, 15 2021).

#### 6.4. SAMPLE SIZE (POWER-)

According to estimates on March, 23 2020 1350 people meet eligibility criteria.

We will require 675 participants in each cohort to analyse the effects of SARS-CoV-2 on immunity. The sample will be representative of the study population.

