##### *Sample Size Estimation*

In a one-way ANOVA study, sample sizes of 522, and 522 are obtained from the 2 groups whose means are to be compared. The total sample of 1044 subjects achieves 90% power to detect differences among the means versus the alternative of equal means using an F test with a 0.05 significance level. The size of the variation in the means is represented by the effect size  $\eta^2 = \sigma_m^2 / (\sigma_m^2 + \sigma^2)$ , which is 0.01 [10-13]

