##### *Dropout-Inflated Sample Size*

Average Group Sample Size n	Group	Dropout Rate	Sample Size Ni	Dropout-Inflated Enrollment Sample Size Ni'	Expected Number of Dropouts Di
522	1-2	10%	522	580	58
	Total		1044	1160	116

Average Group Sample Size n	Group	Dropout Rate	Sample Size Ni	Dropout-Inflated Enrollment Sample Size Ni'	Expected Number of Dropouts Di
522,00	1 - 2	10%	522	580	58
	Total		1044	1160	116

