#### 6.5.1. RECRUITMENT

The Basic Prevention Unit of Northern Metropolitan Area of Barcelona (Primary Health Care and Hospital), Spain (NM\_BCN) offers HCW to participate in ProHEPIC-19 study, if they accept; the researchers of ProHEPiC-19 contact these participants.

Eligible participants interested in the study, are accurately informed about the ProHEPiC-19 protocol, and signed informed consent to participate.

Participants complete several clinical questionnaires and immune clinical determination at baseline, 7 days, 15 days, 3, 6, 9 and 12, 16, 20, 24 months after the beginning of the study. (see Table 2)

Participant data files will be stored in numerical order (code system) and in a secure and accessible place and manner. Participant files will be maintained in storage for a period of 15 years after completion of the study.

Anonymised demographic data will be collected for those participants who decline to take part in the project, to assess the external validity of the recruited sample of participants.

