**Primary Outcome Measure:**

1. Creation prospective cohort of health care workers

Include 675 exposed HCW participants and 675 infected HCW participants against SARS-CoV-2, cohorts will be compared at each time point in terms of sociodemographic, epidemiological, clinical, and immunological information available. an exploratory bivariate analysis will be performed using the tests of Chi Square, ANOVA, Kruskall-Walis, depending on the application conditions assumptions.

[Time Frame: Baseline, to 12 months after the beginning of the study]

2. Cohort description demografics ( age, sex, academic level, housing characteristics, work variables )

Descriptive analysis of the participants will be performed using the number and percentage for categorical variables, and mean and standard deviation or median and quartiles 1 and 3 for quantitative variables, an exploratory bivariate analysis will be performed using the tests of Chi Square, ANOVA, Kruskall-Walis, depending on the application conditions assumptions.

[Time Frame: Baseline, to 12 months after the beginning of the study]

2. Cohort description clinical spectrum (asymptomatic, mild-moderate illness, severe-critical)

Cohort comparison, an exploratory bivariate analysis will be performed using the tests of Chi Square, ANOVA, Kruskall-Walis, depending on the application conditions assumptions.

[Time Frame: Baseline, to 12 months after the beginning of the study]

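### Does the enrolment figure of 675 per cohort conflict with a sample size calculation that gives 580?

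*Combined protocol and SAP*

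**What the plan says.** Section 6.4 opens with a count of the available people, "According to estimates on March, 23 2020 1350 people meet eligibility criteria", and then gives the requirement: "We will require 675 participants in each cohort to analyse the effects of SARS-CoV-2 on immunity". The same figure appears in section 6.1 ("Each cohort will include 675 participants"), in the first primary outcome in sections 5.2.1 and 6.6.2 ("Include 675 exposed HCW participants and 675 infected HCW participants"), and in the Abstract ("For now, the study consists of 1350 participants divided into 2 cohorts").

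The calculation under Sample Size Estimation is a one-way ANOVA with two groups of 522, an F test at the 0.05 level and an effect size of eta-squared 0.01. Its result is "The total sample of 1044 subjects achieves 90% power to detect differences among the means". The table that follows applies 10% dropout. Its column "Dropout-Inflated Enrollment Sample Size" shows 580 per group and 1160 in total. The groups are labelled only 1-2, and no endpoint or time point is given.

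**The concern.** A reader who finds a required number under a heading about power expects the calculation below it to produce that number. Here it produces 580, and nothing links 580 to 675. Because 675 is half of 1350, it may be the size of the available pool and not a statistical need, but the plan does not say so.

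Two things would be at stake. If 675 were a true statistical requirement, the calculation shown would be the wrong one, or some of its inputs would be missing. And because the two groups are not named, the 90% might be taken to cover the hypotheses in section 5.1 on clinical spectrum and sex. Clinical spectrum is defined only within the infected cohort, and the kinetics models that compare spectra and sexes leave out participants who never tested positive.

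**Working it through.** **Inputs**, all from section 6.4: k = 2 equal groups, eta-squared = 0.01, alpha = 0.05, target power 90%, dropout 10%, stated requirement 675 per cohort.

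**Step 1. Reproduce the plan's figure.** Power comes from the noncentral F distribution with (k − 1, N − k) degrees of freedom and noncentrality λ = N × eta-squared / (1 − eta-squared) = N × 0.01/0.99 = N/99.

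- N = 1044: λ = 1044/99 = 10.55, power 0.9005.
- N = 1042 (521 per group): power 0.89996, just short of 90%.

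So 522 per group is the smallest size that reaches 90%, as stated.

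**Step 2. Reproduce the dropout adjustment.** 522 / (1 − 0.10) = 580 per group, so 1160 in total and 116 expected dropouts. This also matches the table.

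**Step 3. Size of the gap.** 675 − 580 = 95 per cohort; 1350 − 1160 = 190 in total; 95/580 = 16.4%.

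**Step 4. Can other ordinary inputs give 675?**

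- 20% dropout: 522/0.80 = 652.5, so 653.
- 25% dropout: 522/0.75 = 696.
- 95% power needs 645 per group; 645/0.90 = 716.7, so 717.
- Exact match: 1 − 522/675 = 22.7% dropout, which the plan does not state.

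None of these gives 675 from a natural choice. The only nearby figure that does is 1350/2 = 675. That origin is an inference.

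**Step 5. What 675 per cohort delivers for the same contrast (eta-squared 0.01).**

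| Analysed in total | λ = N/99 | Power |
|---|---|---|
| 1044 (580 per cohort less 10%) | 10.55 | 0.9005 |
| 1215 (675 per cohort less 10%: 607.5 × 2) | 12.27 | 0.938 |
| 1350 (675 per cohort, no loss) | 13.64 | 0.958 |

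Read the other way, the 22.7% in Step 4 is the dropout that 675 per cohort can absorb before power for this contrast falls below 90%.

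**Step 6. Which groups are meant?** The sentence just before the calculation speaks of 675 in each cohort. Section 6.1 defines exactly two cohorts, healthy and infected. Sections 5.2.1, 6.6.2 and 6.8.1 plan to compare the cohorts with tests that include ANOVA. The two groups are therefore readily identified as the two cohorts. Clinical spectrum has three categories (section 6.5), so a two-group calculation cannot sensibly be read as powering that comparison. Only the endpoint and the time point are truly unstated.

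**The case for a change.** The strongest case for a change has three parts.

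First, 675 is written into the first primary outcome. If enrolment ended between 580 and 675 per cohort, the calculated need would be met while that outcome was missed. This is true, but it does not leave the governing number in doubt. Every statement of enrolment uses 675; 580 appears only as output of the calculation and is nowhere called a target. A target set above a calculated minimum is not a contradiction.

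Second, if 675 is simply half of the eligible pool, the plan appears to assume that nobody refuses, although section 6.5.1 says "Anonymised demographic data will be collected for those participants who decline to take part in the project". This does not stand. Section 6.2.1 makes agreement to take part an inclusion criterion, so people who decline are not eligible under the plan's own definition, and the estimate of 1350 cannot serve as a denominator that includes them. The source population is 7,776 workers, and the Abstract plans to enlarge the cohort until 2024.

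Third, the 90% does not carry over to the comparisons within the infected cohort. As an illustration only, assuming eta-squared 0.01, a single time point and three equal groups of 225, a spectrum comparison among 675 infected participants has about 64% power. The figure is right under those assumptions. However, section 6.4 claims no power for that comparison, the cohort comparisons are labelled exploratory, and the kinetics are to be modelled longitudinally in everyone who ever tested positive, which a single-time-point figure does not describe.

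What stands is narrow: the reason for the extra 95 per cohort, and the endpoint and time point of the powered contrast, are not written down.

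**Conclusion.** No change to the plan. The calculation is correct, and the enrolment figure exceeds its result by 95 per cohort (16%). The two-cohort contrast has about 94% power after 10% dropout and about 96% with none, against a goal of 90%. A team that follows the plan as written recruits to 675 and runs the same analyses whether or not the margin is explained. What is missing is reporting detail that the authors can supply in a sentence: 580 as the calculated minimum, 675 as the target with its reason, and the endpoint and time point of the healthy-versus-infected comparison.

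The power figures assume the plan's eta-squared of 0.01, equal cohorts, equal dropout of 10% in each, and one normal-theory F test at a single time point. Taking the two groups to be the healthy and infected cohorts is a reading of section 6.4 together with section 6.1. The origin of 675 as half of 1350 is plausible but unconfirmed, and the conclusion does not depend on it.
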